1.2.2.5. Pegylated Liposomal Doxorubicin

Doxorubicin is a cytotoxic anthracycline antibiotic isolated from *Streptomyces peucetius* var. *caesius* which has been available since the 1960s. Its main mode of action is to bind with topoisomerase II and DNA, forming a complex which results in lethal double-stranded DNA breaks.²⁵ Pegylated liposomal doxorubicin (PLD) (trade names Doxil[®], Caelyx[®]) is a formulation of liposomal doxorubicin coated in polyethylene glycol (PEG). This hydrophilic coating protects the liposomes from detection by the body's reticular endothelial system, reducing the rate at which the active substance is broken down, and increasing its circulating half-life compared with conventional doxorubicin.²⁵

PLD displayed linear pharmacokinetics over the range of 10 to 20 mg/m². Relative to PLD doses at or below 20 mg/m², the pharmacokinetics of total PLD following a 50 mg/m² PLD dose are nonlinear. At this dose, the elimination half-life of PLD is longer and the clearance lower compared to a 20 mg/m² dose. Converse to the pharmacokinetics of doxorubicin, which displays a large volume of distribution (700-1100 L/m²), the steady-state volume of distribution of PLD is restricted to the vascular fluid volume. The major metabolite of

doxorubicin, doxorubicinol, was detected at negligible levels in patients who received 10 or 20 mg/m² PLD.¹⁶

The most common toxicities of PLD (>20%) are asthenia, fatigue, fever, anorexia, nausea, vomiting, stomatitis, diarrhea, constipation, hand-foot syndrome, rash, neutropenia, and anemia.¹⁶ Acute Infusion-Related Reactions occurred in 11% of patients with solid tumors. Serious, life-threatening, and fatal infusion reactions have been reported. PLD can cause myocardial damage, including congestive heart failure. The risk of cardiotoxicity is 11% when the lifetime cumulative anthracycline dose (not limited to PLD) approaches 450-550 mg/m².

Single-agent PLD has been extensively studied in platinum-resistant ovarian cancer, demonstrating an objective response rate (ORR) of 10-20%, median PFS of 2.1-3.7 months, and OS ranging from 8.4 to 16.8 months.^{20,21,22,23,24,25}

Complete information for PLD may be found in the single reference safety document (SRSD), which for this study is the Caelyx SmPC.

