5.2.8.2. PLD: Infusion-Related Reactions (Hypersensitivity Reactions)

Serious and sometimes life-threatening infusion-related reactions characterized by one of more of the following symptoms can occur with PLD: flushing, shortness of breath, facial swelling, headache, chills, chest pain, back pain, tightness in the chest and throat, fever, tachycardia, pruritus, rash, cyanosis, syncope, bronchospasm, asthma, apnea, and hypotension. The majority of the infusion-related events occur during the first infusion.

Ensure that medications to treat infusion-related reactions and cardiopulmonary resuscitative equipment are available for immediate use prior to initiation of PLD. Initiate PLD infusion at a rate of 1 mg/min and increase rate as tolerated. In the event of an infusion-related reaction, temporarily stop the drug until resolution, then resume at a reduced infusion rate. Discontinue PLD infusion for serious or life-threatening infusion-related reactions.

In order to mitigate PLD infusion-related reactions, a premedication regimen as described in [Section 5.2.3.1](#) may be administered.

PLD treatment modifications for infusion-related reactions are presented in Table 8.

Table 8. PLD Single Agent and PLD-avelumab Combination: Treatment Modification for PLD Infusion-Related Reactions

NCI-CTCAE Grade	Treatment Modification for PLD (both PLD single agent and PLD-avelumab combination*)
Grade 1 – mild Mild transient reaction; infusion interruption not indicated; intervention not indicated.	Temporarily stop PLD until resolution then resume at a reduced infusion rate per local practice.**
Grade 2 – moderate Therapy or infusion interruption indicated but responds promptly to symptomatic treatment (eg, antihistamines, NSAIDs, narcotics, i.v. fluids); prophylactic medications indicated for ≤24 hours.	Temporarily stop PLD until resolution then resume at a reduced infusion rate per local practice.**
Grade 3 or Grade 4 – severe or life-threatening Grade 3: Prolonged (eg, not rapidly responsive to symptomatic medication and/or brief interruption of infusion); recurrence of symptoms following initial improvement; hospitalization indicated for clinical sequelae. Grade 4: Life-threatening consequences; urgent intervention indicated.	Permanently discontinue PLD infusion.**

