6.2.6. Endpoints for immunogenicity data of avelumab

All analyses described below are performed by treatment arm containing avelumab (Arm A and Arm B), and for the avelumab-containing treatment arms combined unless otherwise specified.

Blood samples for avelumab immunogenicity testing will be collected within 2 hours before the start of the avelumab infusion on Day 1 of Cycles 1 through 4. Thereafter, a sample will be collected on Day 1 prior to avelumab infusion in Cycles 5, 6, 9, 12, 15, 18, 21 24 and at the End of Treatment. An additional sample must be collected at 30 days after the last dose of avelumab.

Samples positive for ADA will be analyzed for titer and may be analyzed for nAb. As of the finalization of this SAP, the nAb assay is not yet available, therefore the analyses of nAb data described in the following sections will only be conducted contingent upon assay and data availability at the time of reporting.

Patients will be characterized into different ADA categories based on the criteria defined in [Table 13](#).

Table 13 Patients Characterized Based on Anti-Drug Antibody Results (ADA Status)

Category	Definition	Subjects at Risk (Denominator for Incidence)
ADA never-positive	No positive ADA results at any time point; ADA-negative patients (titer < cutpoint)	Number of patients with at least one valid ADA result at any time point
ADA ever-positive	At least one positive ADA result at any time point; ADA-positive patients (titer ≥ cutpoint)	Number of patients with at least one valid ADA result at any time point
Baseline ADA positive	A positive ADA result at baseline	Number of patients with valid baseline ADA result
Treatment-boosted ADA	A positive ADA result at baseline and the titer ≥ 8×baseline titer at least once after treatment with avelumab	Number of patients with valid baseline ADA results and at least one valid post-baseline ADA result
Treatment-induced ADA	Patient is ADA-negative at baseline and has at least one positive post-baseline ADA result; or if patient does not have a baseline sample, the patient has at least one positive past-baseline ADA result	Number of patients with at least one valid post-baseline ADA result and without positive baseline ADA result (including missing, NR)

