The frequency (number and percentage) of patients with each of the following will be presented by ADA status.

- TEAEs, by SOC and PT

- TEAEs leading to dose reduction of avelumab, by SOC and PT
- TEAEs leading to discontinuation of avelumab, by SOC and PT
- TEAEs leading to discontinuation of study treatment by SOC and PT
- Grade ≥ 3 TEAEs, by SOC and PT
- SAEs, by SOC and PT
- IRRs, by PT

For patients who had at least one IRR and have treatment-induced ADA, time related to first onset of an IRR (infusion 1, infusion 2, infusion 3, infusion 4 or later) will be summarized taking into account whether the IRR occurred on or after the first ADA positive assessment or whether the IRR occurred before the first ADA positive assessment.

As data permit, the analyses described above will be repeated for nAb.

Efficacy and immunogenicity status

For the ADA ever-positive patients, a listing will be prepared with patient ID, start and stop of avelumab treatment, date of first positive ADA result, time to ADA response, duration of ADA response, date of last ADA positive result, BOR, DR, PFS time or censoring time and reason for censoring, and OS time or censoring time and reason for censoring. If applicable, date of first positive nAb result, time to nAb response, duration of nAb response, date of last nAb positive result will also be presented. Tumor-related endpoints will be presented based on BICR assessment and based on Investigator assessment.

For the ADA ever-positive patients, the percent change from baseline in target lesions as well as the first occurrence of a new lesion and patient off avelumab treatment will be displayed against time point (weeks) in a line plot. Additional symbols will indicate the first and last ADA positive result and, if applicable, the first and last nAb positive result. Plot will be presented separately based on BICR assessment and based on Investigator assessment.

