	
IRR can be associated with the first IV drug and/or subsequent IV drugs that are administered in combination. Without loss of generality assume triplet IV with D₁ administered first then D₂ then D₃. The IV study drug or drugs associated with the IRR need to be identified in the analysis data set to enable subsequent analysis.
 
The following are not sequential and an AE can be classified as an IRR associated with multiple D_j from one or more of I, II, III, IV, V below:
 
I - If the AE meets [1 AND 2A1] for a D_j then the AE is classified as an IRR associated with the D_j that meets the 2A1 criterion
 
II - If the AE meets [1 AND 2A2] for a D_j then the AE is classified as an IRR associated with the D_j and associated with D_{j+1} that meets the 2A2 criterion
 
III - If the AE meets [3 AND 4B] for any D_j then the AE is classified as an IRR associated with all D_j that meet the 4B criterion.
 
IV- If the AE meets [3 AND 4A1] for a D_j then the AE is classified as an IRR associated with the D_j that meets the 4A1 criterion
 
V- If the AE meets [3 AND 4A2] for a D_j then the AE is classified as an IRR associated with the D_j and associated with D_{j+1} that meets the 4A2 criterion

1	PT is included in the 'IRRs SIGNS and SYMPTOMS' list
2A1	
 • AE onset date = date of infusion of study drug D_j AND • AE timing related to study drug D_j ('DURING', 'AFTER') AND • [AE timing related to study drug D_{j+1} ('BEFORE') OR AE onset date < date of infusion of study drug D_{j+1}] AND • AE outcome in ('RECOVERED/RESOLVED', 'RECOVERED/RESOLVED WITH SEQUELAE', 'RECOVERING/RESOLVING') AND • AE end date – AE onset date <=2
2A2	
 • AE onset date = date of infusion of study drug D_j AND • AE timing related to study drug D_j ('DURING', 'AFTER') AND • AE timing related to study drug D_{j+1} ('DURING', 'AFTER') AND • AE outcome in ('RECOVERED/RESOLVED', 'RECOVERED/RESOLVED WITH SEQUELAE', 'RECOVERING/RESOLVING') AND • AE end date – AE onset date <=2
3	PT is included in the 'IRRs CORE' list
4A1	
 • AE onset date = date of infusion of study drug D_j AND • AE timing related to study drug D_j ('DURING', 'AFTER') AND • [AE timing related to study drug D_{j+1} ('BEFORE') OR AE onset date < date of infusion of study drug D_{j+1}]

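### SAP 6.2.6.3 relates infusion reactions to anti-avelumab antibodies without the drug attribution that Table 18 requires, so PLD-only reactions enter the Arm B and combined-arm tables

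*SAP*

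**What the plan says.** **Attribution rule (SAP Appendix 2, Table 18).** When IV drugs are given in combination: "The IV study drug or drugs associated with the IRR need to be identified in the analysis data set to enable subsequent analysis". Under criteria 2A1 and 4A1, a reaction that starts during or after one drug but before the next is assigned to the earlier drug only. Under 2A2 and 4A2, a same-day reaction that starts during or after the second drug is assigned to both. Under 4B, a core-term reaction on the following day goes to every drug infused the day before. The table states: "The following are not sequential and an AE can be classified as an IRR associated with multiple" drugs.

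**Infusion order (Protocol 3.1.2 and 5.2.3.1).** In Arm B, PLD precedes avelumab on shared days, and no gap between the two infusions is required.

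**Use in the immunogenicity analysis (SAP 6.2.6 and 6.2.6.3).** On arms: "All analyses described below are performed by treatment arm containing avelumab (Arm A and Arm B), and for the avelumab-containing treatment arms combined". The safety list by ADA status has seven rows. Its IRR row is by preferred term with no drug named. Two other rows do name the drug, for example "TEAEs leading to discontinuation of avelumab, by SOC and PT". A separate timing summary follows: "For patients who had at least one IRR and have treatment-induced ADA, time related to first onset of an IRR". It is split by "whether the IRR occurred on or after the first ADA positive assessment or whether the IRR occurred before the first ADA positive assessment". Both items are repeated for neutralizing antibodies (nAb) as data permit.

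**Background rates.** For PLD, Protocol 1.2.2.5 says: "Acute Infusion-Related Reactions occurred in 11% of patients with solid tumors". Protocol 5.2.8.2 adds: "The majority of the infusion-related events occur during the first infusion". For avelumab, Protocol 1.2.2.2 gives 49/480 (10.2%) overall and 33/440 (7.5%) under mandatory premedication. Onset was after infusion 1 in 30 patients and after infusion 2 in 16.

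**The concern.** An analysis of IRRs by ADA status asks whether antibodies to avelumab go with more reactions to avelumab. A reaction that began before avelumab was hung that day, and that the SAP's own rules assign to PLD alone, does not bear on that question. It is reasonable to expect such reactions to be unrelated to anti-avelumab antibodies, although the documents do not say so. They would then add a similar background rate to ADA-positive and ADA-negative patients and pull the two groups' rates together in relative terms.

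The background is not negligible, because the quoted PLD rate is about the size of avelumab's own. An Arm B result weakened in this way, set beside an undiluted Arm A result, could also be misread as PLD changing the relation between ADA and infusion reactions.

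**Working it through.** The plan gives no figure for this association, so there is none to reproduce. The background rates check: 49/480 = 10.2% and 33/440 = 7.5%.

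**Inputs from the documents**
- Average avelumab IRR risk, m: 10.2% or 7.5%.
- PLD IRR rate: 11%.

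**Assumptions, not in the documents**
- True ADA risk ratio R: 2 or 3.
- ADA prevalence p: 5% or 20%.
- Share of the 11% that Table 18 would label PLD-only: 25%, 50% or 100%, so q = 2.75%, 5.5% or 11%.
- PLD-only reactions are independent of ADA status and of avelumab reactions.
- Arms A and B are of equal size.

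**Formulas**
- Avelumab risk if ADA-negative: b = m / (pR + 1 − p). If ADA-positive: a = R·b.
- Arm B risk in each group: 1 − (1 − a)(1 − q) and 1 − (1 − b)(1 − q).
- Combined arms: the average of Arm A (a or b) and Arm B.

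**Strong end (m = 7.5%, p = 20%, q = 11%)**
- R = 2: b = 0.075/1.2 = 0.0625 and a = 0.125. Arm B: 0.2213 vs 0.1656, ratio 1.34. Combined: 0.1731 vs 0.1141, ratio 1.52.
- R = 3: b = 0.075/1.4 = 0.0536 and a = 0.1607. Arm B: 0.2530 vs 0.1577, ratio 1.60. Combined: 0.2069 vs 0.1056, ratio 1.96.

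**Weak end (m = 10.2%, p = 5%, q = 2.75%)**
- R = 2: b = 0.102/1.05 = 0.0971 and a = 0.1943. Arm B: 0.2164 vs 0.1220, ratio 1.77. Combined: 0.2054 vs 0.1096, ratio 1.87.
- R = 3: b = 0.102/1.10 = 0.0927 and a = 0.2782. Arm B: 0.2980 vs 0.1177, ratio 2.53. Combined: 0.2881 vs 0.1052, ratio 2.74.

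| True ratio | Arm A | Arm B | Combined |
|---|---|---|---|
| 2 | 2 | 1.34 to 1.77 | 1.52 to 1.87 |
| 3 | 3 | 1.60 to 2.53 | 1.96 to 2.74 |

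**Risk difference.** In Arm B it is (a − b)(1 − q), so it shrinks by q: 2.75% to 11%.

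**PLD-only share of Arm B reactors.** This is (1 − m)q / [1 − (1 − m)(1 − q)]. It runs from 0.0247/0.1267 = 19% (m = 10.2%, q = 2.75%) to 0.1018/0.1768 = 58% (m = 7.5%, q = 11%).

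**Timing.** ADA is sampled before the avelumab infusion on Day 1 of Cycles 1 to 4 (SAP 6.2.6). The first post-baseline sample is therefore at Cycle 2 Day 1, after avelumab infusions 1 and 2. From the phase 1 figures, e = (30 + 16)/49 = 94% of avelumab reactors had onset before that point. Let s be the assumed share of PLD reactions that are equally early. The share of reactors whose first IRR comes before Cycle 2 Day 1 is

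1 − [(1 − m·e)(1 − q·s) − (1 − m)(1 − q)] / [1 − (1 − m)(1 − q)].

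Over the same m and q:
- s = 100%: 95% to 98%
- s = 80%: 86% to 91%
- s = 60%: 75% to 87%

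The comparison value without PLD reactions is 94%, so the share can move either way.

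**The case against.** The strongest reply has five parts.

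- **Arm A is reported on its own.** It contains no PLD, so an undiluted table is already planned. This stands: the defect is confined to Arm B and the combined arms.
- **The SAP plans counts and percentages, with no ratio and no test.** On the difference scale the loss is small. This also stands and limits the importance, although a reader of two percentages may well compare them as a ratio.
- **The unrestricted IRR row follows the list's usual pattern.** Only two of the seven rows name avelumab, and both concern action taken on a drug. That is fair. The case rests on Table 18 requiring the attribution, not on the neighbouring rows.
- **Not all of the 11% would be PLD-only.** A reader might infer that Table 18 gives each reaction to one drug, and so that PLD accounts for about half of Arm B reactors. The documents do not support that. Same-day reactions during or after avelumab, and next-day core-term reactions, go to both drugs. The 11% is also a general solid-tumour figure, while this trial starts PLD at 1 mg/min to reduce reactions (Protocol 1.2.4.2). This is why a range is shown.
- **Timing.** A reader might infer that PLD reactions push the timing table towards IRRs occurring before ADA. Within one patient, adding PLD reactions can only move the first IRR earlier. Across patients the direction is open, because avelumab's own reactions are already so early and the protocol says only that a majority of PLD reactions come at the first infusion.

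**Conclusion.** The point holds as a limited one. As written, 6.2.6.3 counts reactions that the SAP's own rules label PLD-only when it relates IRRs to anti-avelumab antibodies in Arm B and the combined arms. Every scenario examined weakens the apparent ratio, by an amount that depends mainly on how much of the PLD rate is PLD-only. The size rests on the assumed ADA risk ratios and prevalence, and on PLD reactions being independent of ADA status. For the timing summary, the documents support only that it mixes in PLD reactions.

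It would go too far to infer that the immunogenicity safety analysis as a whole is unreliable or that a main result is touched. These are descriptive secondary tables, and no primary endpoint, alpha or test depends on them. This is a cheap improvement rather than a serious fault.

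**What to change.** In SAP 6.2.6.3, for Arm B and for Arms A and B combined, define three items as IRRs associated with avelumab, alone or together with PLD, under Appendix 2: the IRR-by-ADA table, the IRR-by-nAb table and the first-IRR timing summary. Show PLD-only or all-IRR counts in a separate row, so that nothing drops out of view. The overall IRR tables in 6.6.4 stay as they are.

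The cost is one sentence in the SAP and one filter or extra row in the program, using an attribution that Table 18 already requires. Protocol Section 9 says the final analysis is complete, so the change can be made as supplementary tables. The remaining limitation is that reactions assigned to both drugs stay in, so some PLD reactions will still be counted.
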